### **11.3 Data handling and analysis**

A bespoke password protected “Red Pill” database designed by sealedenvelope.com (limited to nominated staff recorded on the delegation log by the CI) will be used for data entry and storage of anonymised patient records and CRF data. This database will be hosted on a secure server at sealedenvelope. All source data (other than data collected from the SCRAM-X bracelet) will be securely stored at site with access limited to only authorised staff. Data from the SCRAM-X bracelet will be stored on a secure drive at the Psychopharmacology and Addiction Research Centre, [name]. Automated data (SCRAM-X, pattern recognition task, stop signal task) will be kept on an encrypted memory stick with the source data.

The CRF and trial specific documents held by the researcher will be stored securely with access restricted and limited to nominated research staff recorded on the delegation log and in accordance with the data protection act 1998, UCL Information Security Policy and Trust Information Governance Policy. Electronic and questionnaire source data will be stored in a password protected Microsoft Access database. The Red Pill database will keep a record of all changes to and access of the database. All data and audit log files from the Red Pill eCRF are backed up daily to tape within the data-centre with a two week retention period. Since the databases and log files are cumulative (no deletion), it is not necessary to keep backups beyond this retention period. In addition all data and log files are replicated immediately and continuously to a remote server for off-site storage.

The CRF will be accessible by the research team through access codes on the password protective electronic database site (the detailed arrangements will be in the data management SOP). The data will be available for download by the trial statistician and nominated members of the study team over a CTPS encrypted protocol. Once downloaded, data will be stored on a password protected networked drive at the University of Exeter. At the end of the study, sites will file copies of the eCRFs for their patients on an encrypted memory stick for archiving purposes.

The CI will be ultimately responsible for data entry and quality. Trial staff as identified on the delegation log will also be responsible for data entry and quality. Single data entry with quality control checks will be used in the eCRF. Once data has been entered a visual check between what has been entered and the CRF/source data will be made by another member of the research team. Validity checks will be made using dates of testing days against each patient ID. Data stored within the Access database will be entered using Teleform software and then verified by the data manager.

Data analysis will be performed independently of data entry by the trial statistician.

Data will be stored and backed up daily by through the Red Pill service. The drives will be backed up frequently, allowing for data retrieval in the event of data loss. Data transfer and storage will be in accordance with the UK Data Protection Act 1998 as well as UCL Information Security Policy and Trust Information governance policy. Once all data checks and data are completed, the database will be locked and read only. Users can still view the contents of the database and produce reports. The database will also be accessed centrally by the study statistician (on a read only basis) for data analysis and access of the database will be logged in the data transfer log kept in the TMF or the database will be sent by [name] to the statistician electronically as read only through a secure process of password protected encryption and this will be documented in the data transfer log kept in the TMF.

## **12 Record keeping and archiving**

Archiving will be authorised by the Sponsor following submission of the end of study report. The Chief Investigator will be responsible for the secure archiving of essential trial documents and the trial database as per their trust/university policy. All essential documents will be archived for a minimum of 25 years after completion of trial. The investigator or a delegate at site is responsible for the secure archiving of essential site trial documents as per local trust policy arrangements. Destruction of essential documents will require authorisation from the Sponsor.

## **13 Statistical Considerations**

[name] is the trial statistician who will be responsible for all statistical aspects of the trial from design through to analysis and dissemination.

### **13.1 Outcomes**

#### ***13.1.1 Primary outcomes***

Relapse rates at 6 months

Percentage Days Abstinent at 6 months

#### ***13.1.2 Secondary outcomes***

- Number of days of continuous abstinence at 3 months ( Time-line follow back)
- Percentage days abstinent at 3 months (timeline follow-back)
- State mood (Profile of Mood states)
- Depression (Beck Depression Inventory; Hamilton Depression Scale)
- Anxiety (Speilberger Trait Anxiety Inventory)
- Psychotic symptoms (Brief Psychiatric Rating Scale; Psychotomimetic States Inventory)
- Cigarette smoking (Fagerstrom Smoking)
- Craving (Visual Aanalogue Scales)
- Quality of Life (SF-12)
- Episodic Memory (Prose Recall)
- Delay Discounting (monetary choice questionnaire)
- Response Inhibition (Stop Signal Reaction time)
- Working Memory (digit span WAIS-IV)
- Hippocampal Functioning (Pattern Recognition Test)
- Adverse Effects (Adverse Effects VAS)
- Alcohol Craving Questionnaire - short-form (ACQ-NOW)

### **13.2 Sample size and recruitment**

#### ***13.2.1 Sample size calculation***

As this is a proof of concept study we wish to include the minimum number of subjects, and must balance considerations of feasibility, including

recruitment, whilst providing a reliable early indicator of efficacy that would warrant continuing to a larger trial.

*Our justification of sample size of n=96:*

Following randomisation the patient allocation will be n=24 per cell. Drop-out rates will be minimised with incremental payment schedules as we have used in previous studies where we have achieved high retention rates in difficult populations (e.g. [93]). It is anticipated that wearing the SCRAM-X bracelets may also reduce drop-out rates as they are designed to increase compliance with treatment programmes in offending populations (Compliance Monitoring Systems, LLP). However, we have adopted a very conservative estimated 50% drop-out. If this level of drop-out is observed, that will leave n=12 in each individual cell, with a total of n=24 patients having been administered ketamine and n=24 placebo.

With n=24 people in each drug arm we will be able to estimate a decrease in the relapse rate from 50% in patients given placebo to 25% (90% CI: 3% to 47%) in patients given ketamine.

A decrease of 25% in relapse would be clinically important, and lower than that observed in the preliminary work ([33]: 42%); it would clearly suggest that further investigation is warranted. Our confidence intervals are relatively broad as this is a proof of concept study and we wish to minimize the numbers of subjects involved.

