### **13.3.2 Primary outcome analysis**

There are two primary outcomes: (i) proportion relapsed (recommenced using alcohol) at 6-month follow-up; and (ii) percentage of days abstinent at 6-month follow-up (the denominator being 175 days). The proportion of relapsed participants at 6-month follow-up will be reported as a percentage for each arm, as well as for the ketamine arms combined and

the psychotherapy arms combined. Although no formal power calculations for a between-group analysis have been performed, the proportion of relapsed participants at 6-month follow-up will be expressed as a relative risk (RR) with a 95% confidence interval for the following comparisons: (i) all ketamine participants versus all non-ketamine participants; (ii) ketamine + psychotherapy participants versus ketamine + non-psychotherapy participants; and (iii) ketamine + psychotherapy participants vs. placebo + no psychotherapy participants. These analyses are purely exploratory and should be viewed with caution both in the light of lack of power and multiple testing. Percentage of days abstinent at 6-month follow-up will be reported descriptively in the same way by arm and combination of arms; additionally, the between-group mean differences and 95% confidence intervals will be reported for the comparisons set out above; again, these analyses should be regarded as exploratory. The primary analysis will be an intention-to-treat (ITT) complete case analysis including all randomised participants. A secondary analysis will be conducted including only those participants deemed to have completed to a sufficient degree their allocated interventions, that is, a per protocol analysis. All analyses will be performed by a statistician who is blinded to the treatment allocations and will be performed using Stata v.13.

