6.4 Presentation of inferential analyses

For the inferential analyses, the point estimate for the between arm comparison and 95% confidence interval will be reported. Due to the feasibility nature of the study, and the lack of formal power calculation, no p -values will be reported.

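### The sample-size justification states its precision at 90%, but every planned comparison reports 95% intervals, which at the assumed 50% drop-out are wider and include no effect

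*Protocol*

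**What the plan says.** Protocol 13.2.1 randomises 24 patients to each of four cells, so 48 per drug group. It then allows for heavy loss: "However, we have adopted a very conservative estimated 50% drop-out". That leaves the basis of the justification: "With n=24 people in each drug arm", the trial could estimate "a decrease in the relapse rate from 50% in patients given placebo" "to 25% (90% CI: 3% to 47%) in patients given ketamine". The section calls this fall clinically important and smaller than the 42% seen in the preliminary work, and adds that "it would clearly suggest that further investigation is warranted". It also concedes that its intervals are fairly wide.

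The analysis sections use a different level. In Protocol 13.3.2 relapse at 6 months "will be expressed as a relative risk (RR) with a 95% confidence interval for the following comparisons". Protocol 13.3.3 and the statistical paragraph of the protocol Summary also specify 95%. SAP 4.5 does the same, SAP 6.4 says that "the point estimate for the between arm comparison and 95% confidence interval will be reported", without p-values, and the shells of SAP Tables 4 to 8 are headed 95% CI. Neither document plans a 90% interval or explains why 90% was used in 13.2.1.

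SAP 4.6 restates the justification as a 95% CI width of 37 percentage points for a 25% relapse rate on ketamine. It refers to Protocol 13.2.1, which contains no such figure.

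**The concern.** When a sample size is justified by precision rather than power, the quoted interval is the whole argument. It should be the interval the reader will later see. Here the only interval offered has its lower limit above zero, and it is at a level that no results table will show. Because the SAP reports no p-values, the 95% interval will be the only expression of uncertainty for the primary comparison.

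At stake is how the sponsor, funder or a later reader understands what this sample can show. Someone relying on 13.2.1 would expect the hoped-for 25-point fall to come with an interval clear of zero. If half the patients are lost, the reported interval for that same result would include no effect on both the difference scale and the planned relative-risk scale.

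**Working it through.** **Inputs**
- Relapse 50% on placebo and 25% on ketamine (Protocol 13.2.1).
- 24 analysed per drug group, from 48 randomised and 50% drop-out (Protocol 13.2.1). The expected counts are 12/24 and 6/24.
- Level 90% in Protocol 13.2.1; level 95% in Protocol 13.3.2 and SAP 6.4.
- Assumption: unadjusted intervals. SAP 6.3 adjusts for site, but gives no figure that would allow for this here.

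**1. Reproduce the printed interval**

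SE of the difference = √(0.5×0.5/24 + 0.25×0.75/24) = √(0.4375/24) = 0.1350.

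90%: 25 ± 1.645 × 13.50 = 2.8 to 47.2 points, width 44.4.

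This rounds to the printed 3% to 47%. So the printed interval is a simple (unpooled Wald) interval for the difference between groups, not for the ketamine rate. Other methods at 90% do not match: pooled 2.0 to 48.0, Newcombe 2.0 to 44.6, continuity-corrected -1.4 to 51.4.

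**2. Same inputs at the planned level**

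95%: 25 ± 1.96 × 13.50 = -1.5 to 51.5 points, width 52.9.

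The choice of method does not matter: pooled -2.4 to 52.4, Newcombe -2.2 to 47.7, continuity-corrected -5.6 to 55.6. All include zero.

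**3. The planned scale, relative risk**

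RR = 0.25/0.50 = 0.50.

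SE(log RR) = √(1/6 − 1/24 + 1/12 − 1/24) = √(4/24) = 0.408.

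- 90%: 0.50 × exp(±1.645 × 0.408) = 0.26 to 0.98.
- 95%: 0.50 × exp(±1.96 × 0.408) = 0.22 to 1.11.

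**4. How far this depends on drop-out**

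With n analysed per group at the same rates, SE of the difference = √(0.4375/n) and SE(log RR) = 2/√n.

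| Analysed per group | Drop-out | 95% CI, difference (points) | 95% CI, RR |
|---|---|---|---|
| 24 | 50% | -1.5 to 51.5 | 0.22 to 1.11 |
| 27 | 44% | lower limit 0.05 | upper limit 1.06 |
| 32 | 33% | lower limit 2.1 | upper limit 0.9998 |
| 48 | 0% | 6.3 to 43.7 | 0.28 to 0.88 |

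The 95% interval for the difference first excludes zero at 27 per group. The 95% interval for the RR first excludes 1 at 32 per group.

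**5. Does SAP 4.6 already supply the 95% figure?**

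Its width is 37 points. The between-group 95% width at 24 per group is 52.9, so it is not that quantity. Two other quantities round to 37:
- the exact 95% interval for the single ketamine rate 6/24, which is 9.8% to 46.7%, width 36.9;
- the 95% interval for the difference with no drop-out, 6.3 to 43.7, width 37.4.

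The SAP does not say which was used.

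**6. A different placebo rate**

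Protocol 2.1 cites relapse of about 70% at 6 months. Assuming 70% versus 45%, which is the same 25-point fall, 24 per group gives 2.3 to 47.7 at 90% and -2.1 to 52.1 at 95%. The pattern is unchanged.

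**The case against.** The defence is substantial and most of it stands.

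- *The printed interval is right.* A reader might infer an arithmetic error. There is none: the 90% interval reproduces and is openly labelled 90%.
- *No decision rests on excluding zero.* A reader might infer that the go/no-go reading reverses when the level changes. The documents contain no such rule. In 13.2.1 the statement that "it would clearly suggest that further investigation is warranted" has the 25-point fall itself as its subject, and is tied to the fall's clinical importance and to the preliminary 42%, not to the lower limit of an interval. The only numerical stopping criterion is loss to follow-up in the ketamine groups at 3 months (Protocol 13.5, SAP 6.1).
- *The comparisons are labelled exploratory.* A reader might infer a failed power calculation. Protocol 13.3.2 and SAP 4.5 and 4.6 say that no formal power calculation was made, or that power is lacking, and ask for caution.
- *The 24 per group is a pessimistic case.* A reader might infer that the reported interval will cross no effect whenever the hoped-for result is seen. That holds only near the assumed 50% drop-out, which the protocol itself calls very conservative. With better retention it ceases to be true.
- *The SAP already gives a 95% figure.* It does, but its 37 points is not the width of the between-group interval at 24 per group, and the protocol section it refers to does not contain it. This part of the defence fails.

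What remains is narrow. Conceding that intervals are wide does not tell the reader that the quoted level differs from the one to be reported, or what the reported interval would look like on the same assumptions.

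**Conclusion.** The point holds as a mismatch of confidence level. At 50% versus 25% relapse and 24 analysed per drug group, Protocol 13.2.1 states a width of 44 points with a lower limit of about 3. The planned 95% level gives a width of 53 points with a lower limit of -1.5, and RR 0.50 with limits 0.22 and 1.11.

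The size of the problem is about 8.5 points of interval width (52.9 − 44.4) and the loss of a lower limit above zero. It rests on the protocol's own rates, on 50% drop-out, and on unadjusted intervals. It goes away for the difference from 27 per group and for the relative risk from 32 per group. No planned estimate or results table is wrong, and the sample size is not shown to be inadequate for a proof-of-concept trial.

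**What to change.** In Protocol 13.2.1, restate the precision at 95% and show both ends of the retention range:
- 50% drop-out, 24 per group: -1.5 to 51.5 points; RR 0.50, 0.22 to 1.11;
- no drop-out, 48 per group: 6.3 to 43.7 points; RR 0.50, 0.28 to 0.88.

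Add one sentence saying that at 50% drop-out the reported interval would include no effect even if the 25-point fall is observed. Make SAP 4.6 agree: say which quantity and which number analysed the 37-point width refers to, or replace it with the figures above.

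Alternatively, if 90% is the intended level for the proof-of-concept reading, say so before unblinding and add the 90% interval for ketamine versus placebo to SAP Tables 4 to 6, beside the 95% interval. SAP 4.6 would still need to be reconciled with 13.2.1. Choosing 90% after results are known would look driven by the data.

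The cost is a few sentences and, on the second route, one extra interval in three tables. Sample size, conduct and patient burden do not change. The downside of the first route is a less favourable statement of precision.

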### **13.2.2 Planned recruitment rate**

The recruitment period will be 4 years. Approximately 540 patients every 12 months pass through the detoxification services in the NHS trusts we will recruit from, therefore we consider the recruitment of these 96 individuals over 24 months to be achievable.

## **13.3 Statistical analysis plan**

### **13.3.1 Summary of baseline data and flow of patients**

We will assess the comparability of the randomised groups including each factor including demographics and the baseline assessments described in section 7. We plan to produce a consort flow diagram (<http://www.consort-statement.org/>).

### **13.3.2 Primary outcome analysis**

There are two primary outcomes: (i) proportion relapsed (recommenced using alcohol) at 6-month follow-up; and (ii) percentage of days abstinent at 6-month follow-up (the denominator being 175 days). The proportion of relapsed participants at 6-month follow-up will be reported as a percentage for each arm, as well as for the ketamine arms combined and

the psychotherapy arms combined. Although no formal power calculations for a between-group analysis have been performed, the proportion of relapsed participants at 6-month follow-up will be expressed as a relative risk (RR) with a 95% confidence interval for the following comparisons: (i) all ketamine participants versus all non-ketamine participants; (ii) ketamine + psychotherapy participants versus ketamine + non-psychotherapy participants; and (iii) ketamine + psychotherapy participants vs. placebo + no psychotherapy participants. These analyses are purely exploratory and should be viewed with caution both in the light of lack of power and multiple testing. Percentage of days abstinent at 6-month follow-up will be reported descriptively in the same way by arm and combination of arms; additionally, the between-group mean differences and 95% confidence intervals will be reported for the comparisons set out above; again, these analyses should be regarded as exploratory. The primary analysis will be an intention-to-treat (ITT) complete case analysis including all randomised participants. A secondary analysis will be conducted including only those participants deemed to have completed to a sufficient degree their allocated interventions, that is, a per protocol analysis. All analyses will be performed by a statistician who is blinded to the treatment allocations and will be performed using Stata v.13.

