## Summary

**Title:** A phase II, randomised, double-blind, placebo-controlled, multi-site, parallel group clinical trial to examine ketamine as a pharmacological treatment for alcohol dependence in an alcohol dependent population.

**Short title:** KARE: Ketamine for the reduction of Alcoholic Relapse  
**Trial medication:** Ketamine Hydrochloride and Placebo (Saline)

**Phase of trial:** Phase II

**Objectives:** Primary objectives:

1) To obtain preliminary data on whether ketamine is effective in promoting and prolonging abstinence in alcohol dependent patients following detoxification.

2) To assess safety and tolerability of ketamine in alcohol dependence

Secondary objectives:

1) To make an early assessment on likely compliance to a combined ketamine and relapse prevention based cognitive behavioural therapy (CBT)

2) To obtain preliminary data as to whether ketamine alone is as effective as a combined ketamine and psychotherapy treatment.

**Type of trial:** Phase IIa/b, double-blind, randomised, parallel group, multi-site trial in an alcohol dependent population

**Trial design and methods:** 96 recently detoxified alcoholics will be randomised to receive either 3 sessions of ketamine (0.8 mg/kg IV over 40 minutes) or placebo (50ml Saline 0.9% IV over 40 minutes) plus either manualised psychological therapy or psychoeducation control. Patients will be assessed at 3 and 6 months on a range of psychological and biological variables. The primary endpoint is relapse rate at 6 months. Secondary endpoints include 3 and 6 month percentage days abstinence, tolerability (indicated by drop-out), adverse events, depressive symptoms, craving and quality of life.

Application/exploitation: The findings would have broad application given the worldwide prevalence of alcoholism and associated medical, psychological and social problems.

**Trial duration per participant:** 24 weeks

**Estimated total trial duration:** 30 months

**Planned trial sites:** Multi-site

**Total number of participants planned:** 96

**Main inclusion/exclusion criteria:** Main Inclusion Criteria:

- 18 to 65 years old;
- Meet either a) DSM-5 criteria for moderate/severe alcohol use disorder or b) DSM-IV criteria for alcohol abuse/dependence within the last 12 months;

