### 4 Trial design

#### 4.1 Overall design

[figure not shown]
This non-commercial parallel group, placebo-controlled double blind design aims to make a preliminary assessment of the effectiveness of ketamine in promoting and prolonging abstinence in alcohol dependent patients (Fig. 1). *Why this design was chosen:* A parallel group design is chosen as a crossover would not be feasible with the long time-scales of the study, and given marked carry-over effects that occur in substance-use reduction studies. Three weekly doses of ketamine were chosen as this protocol showed effectiveness in the preliminary studies [33]. This approach has been chosen, rather than a full-scale trial as it is important to confirm the preliminary findings in alcohol dependence. We have chosen to assess outcomes at 3 months and 6 months as from examining other pharmacological and non-pharmacological trials, the largest change in drinking behaviour occurs in the first 3 months and then tails off [40]. However we will follow up again at 6 months to index maintenance of the treatment effect (balancing against the issues of retention of patients in the trial).

For the purpose of this study, Relapse: 5 drinks (drink=13g) in men (8.1units) and 4 drinks (6.5 units) in women on any single occasion and Lapse is defined as 'any other episode of alcohol consumption'.

*Blinding to the IMP:* The trial design will be double blinded. This has been chosen so as to reduce any bias from the power of suggestion of which treatment the patient is received by both the researchers and the patient. The pharmacy or delegated unblinded personnel at both sites will prepare

the syringe for infusion in a blinded fashion so that the administering anaesthetist, psychological researcher and patient are all blind to treatment allocation.

Figure 1: Schematic of overall trial design from recruitment to end of follow up

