The KARE trial is a phase-II randomised trial comparing an active drug intervention (ketamine) with a placebo (saline), and comparing psychotherapy with no psychotherapy (alcohol education). This trial is funded by the Medical Research Council (MRC), and sponsored by University College London (UCL), Sponsor number 13/0253. The EudraCT reference number is 2015-000222-11. The trial has been approved by the South West – Central Bristol Research Ethics Committee (reference number: 15/SW/0312).

This trial aims to gather data regarding the clinical effectiveness of intravenous ketamine (with and without a concurrent psychotherapy intervention) with regard to prevention of relapse (recommencing alcohol use) in participants who are currently abstinent, but who have a current diagnosis of alcohol dependence. The trial will also gather data regarding safety and tolerability of ketamine, and assess compliance with the drug and psychotherapy interventions. Full details of the trial are set out in the KARE trial protocol, Final Version 12, dated 20.01.2020. This statistical analysis plan (SAP) is written in relation to this protocol.

Participants are randomised individually to their combination of ketamine/placebo and psychotherapy/psychoeducation control using a blocking design. Participants are aware of all available treatment options, and that they could potentially be allocated to any of these. The drug intervention is administered by an anaesthetist who is blinded to the drug intervention allocation and also to the therapy intervention. The psychotherapist cannot be blinded to the therapy intervention, but is blinded to the drug intervention. The patient is also blinded to the drug intervention, but is aware of whether they receive psychotherapy or control.

4. Trial information

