5.2 Endpoints

The primary and secondary outcome variables are set out in the Protocol, Final Version 12, 20.01.2020, Section 13.1 (reproduced in Table 2). There are two primary outcomes:

- 1) relapse (defined as 5 drinks (8.1 units alcohol) in men and 4 drinks (6.5 units alcohol) in women on a single occasion) at 6-month follow-up; binary outcome; and
- 2) percentage days abstinent (not using alcohol at all) at 6-month follow-up; percentage, to be analysed as a continuous variable.

The two primary outcomes are to be derived from timeline follow-back.

There are 19 secondary variables, derived from 16 secondary outcomes (Protocol, Final Version 12, 20.01.2020, Section 13.1.2; depression is measured by two variables, Beck Depression Inventory and Hamilton Depression Scale; Short Form Health Survey 12 (SF-12) produces a physical and a mental component scale; psychotic symptoms is measured by two variables, Brief Psychiatric Rating Scale and Psychotomimetic States Inventory).

- 1) maximum number of days of continuous abstinence within the first 3 months (time-line follow back); continuous;
- 2) percentage days abstinent at 3 months (time-line follow back); percentage, to be analysed as a continuous outcome;
- 3) Profile of Mood states; continuous;
- 4) Beck Depression Inventory; continuous;
- 5) Hamilton Depression Scale; continuous;
- 6) Speilberger Trait Anxiety Inventory; continuous;
- 7) Brief Psychiatric Rating Scale; continuous;
- 8) Psychotomimetic States Inventory; continuous;
- 9) Fagerstrom Test of Nicotine Dependence (FTND; smokers only); continuous;
- 10) Alcohol craving (visual analogue scale); continuous;
- 11) Alcohol Craving Questionnaire - short-form (ACQ-NOW);
- 12) Short Form Health Survey 12 (SF-12), physical component scale (PCS); continuous;
- 13) Short Form Health Survey 12 (SF-12), mental component scale (MCS); continuous;
- 14) episodic memory (Prose Recall); continuous;
- 15) delay discounting; continuous;
- 16) response inhibition (Stop Signal Reaction time); continuous;
- 17) working memory; continuous;
- 18) hippocampal functioning (Pattern Recognition Test); continuous; and
- 19) adverse effects (visual analogue scale); continuous.

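### Protocol 13.3.2 and the SAP introduction describe relapse as any resumed drinking, contrary to the 5/4-drink definition in Protocol 4.1 and SAP 5.2; one Summary sentence also lists a primary outcome as secondary

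*Protocol*

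**What the plan says.** **Relapse as any resumed drinking**
- Protocol 13.3.2, the primary-analysis section: "proportion relapsed (recommenced using alcohol) at 6-month follow-up".
- SAP introduction (the unnumbered text before section 4), describing the aim: "prevention of relapse (recommencing alcohol use) in participants who are currently abstinent".

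**Relapse as a drinking threshold**
- Protocol 4.1, defining terms for this study: "Relapse: 5 drinks (drink=13g) in men (8.1units) and 4 drinks (6.5 units) in women on any single occasion". The same sentence continues: "Lapse is defined as 'any other episode of alcohol consumption".
- SAP 5.2: "relapse (defined as 5 drinks (8.1 units alcohol) in men and 4 drinks (6.5 units alcohol) in women on a single occasion) at 6-month follow-up". Table 2 repeats the threshold, and both name timeline follow-back as the source.

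**Silent or unfinished**
- SAP 4.5 and the table shells name relapse without a threshold.
- SAP 5.3, where the derivation belongs, says that details are still to come.
- Protocol 13.2.1 and SAP 4.6 give planning rates of 50% and 25% without saying which definition they use.

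**Status of 6-month percentage days abstinent**
- Protocol Summary, design paragraph: "The primary endpoint is relapse rate at 6 months. Secondary endpoints include 3 and 6 month percentage days abstinence".
- The Summary's statistics paragraph, Protocol 13.1.1 and 13.3.2, and SAP 5.2 all make it a primary outcome.

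**The concern.** The two descriptions of relapse cannot both hold, because Protocol 4.1 creates a category (lapse) that Protocol 13.3.2 counts as relapse. The outcome is binary and is reported as a relative risk, so each participant who drinks only below the threshold changes sides with the definition. The section that disagrees is the protocol's own primary-analysis section, which a reader of the eventual report would consult first.

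No p-values or formal power calculation are planned, so the estimate and its interval are the whole result. The protocol means that result to indicate whether a larger trial is warranted. A report on the any-drinking scale could cite Protocol 13.3.2 in its support, although it would contradict SAP 5.2.

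The Summary sentence raises a smaller version of the same problem: it names one primary endpoint where the rest of the plan has two.

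**Working it through.** **1. Classification of one participant, by text**

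| Drinking in follow-up | Protocol 13.3.2 and SAP introduction | Protocol 4.1, SAP 5.2, Table 2 |
|---|---|---|
| None | not relapsed | not relapsed |
| Some, never reaching 5/4 drinks on one occasion | relapsed | not relapsed (a lapse in Protocol 4.1) |
| 5/4 drinks or more on one occasion | relapsed | relapsed |

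Only the middle row differs.

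**2. The plan's own figures**

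Inputs from Protocol 13.2.1: 50% vs 25%, with 24 per drug arm after 50% drop-out from 96.
- Standard error of the difference = √(0.50×0.50/24 + 0.25×0.75/24) = 0.135.
- 90% interval = 0.25 ± 1.645×0.135 = 2.8 to 47.2 points, against the stated 3% to 47%. This reproduces, as an interval for the difference.
- SAP 4.6 gives a 95% interval width of 37 points for the 25% rate. The exact (Clopper-Pearson) interval for 6/24 is 9.8% to 46.7%, a width of 36.9 points. This also reproduces.

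Neither figure shows which definition the 50% and 25% refer to.

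**3. What the middle row could do (illustration)**

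Take 50% and 25% as the 5/4-drink rates. The share of sub-threshold drinkers is assumed, because the documents give none.

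*Assumption A: a fraction f of all drinkers stays below threshold, equal in both arms.* Any-drinking rate = threshold rate/(1 − f).
- f = 0.1: 0.50/0.9 = 56% and 0.25/0.9 = 28%.
- f = 0.3: 0.50/0.7 = 71% and 0.25/0.7 = 36%.
- The factor 1/(1 − f) cancels, so the relative risk remains 0.50.

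*Assumption B: a fraction q of those not relapsed drinks below threshold, equal in both arms.* Any-drinking rate = p + (1 − p)q.
- q = 0.1: placebo 0.50 + 0.50×0.1 = 55%; ketamine 0.25 + 0.75×0.1 = 32.5%.
- Relative risk = 32.5/55 = 0.59. Difference = 22.5 points, 90% interval −0.4 to 45.4.
- 95% interval for the relative risk (log method, 24 per arm): 0.30 to 1.17, against 0.22 to 1.11 on the 5/4-drink scale. Both include 1.
- The relative risk moves because B implies unequal shares among drinkers: 5/55 = 9% on placebo and 7.5/32.5 = 23% on ketamine.

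**4. The pilot benchmark**

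Protocol 13.2.1 compares the planned reduction with 42% in the preliminary work. Protocol 2.3 reports 66% vs 24% abstinent at one year, and 66 − 24 = 42. The benchmark therefore equals a difference in abstinence, while the SAP endpoint is a drinking threshold. How the pilot measured abstinence lies in a source outside these documents.

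**The case against.** The best defence is that the definition is already settled. Protocol 4.1 defines relapse for this study. SAP 5.2 and Table 2, which specify the endpoint for analysis, repeat that threshold with one data source. The SAP audit trail records that the primary outcome definition in 5.2 was deliberately refined in January 2020. The SAP introduction is a sentence about aims, not an endpoint definition. All inferential analyses are labelled exploratory.

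Much of this stands. A reader might infer that the main result is open, with two definitions of equal standing. The documents do not support that: an analyst who follows SAP 5.2 has one definition. What the defence leaves is that Protocol 13.3.2 states a different endpoint in current text, and that SAP 5.3 does not finish the derivation.

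A reader might also infer that the choice could greatly weaken the treatment contrast. For example, a relative risk of 0.50 on the threshold scale would become 0.75 if any drinking were 45% vs 60%. That needs 20/45 = 44% of ketamine drinkers but only 10/60 = 17% of placebo drinkers to stay below threshold. Nothing in the documents supports such a gap.

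Finally, a reader might take the Summary as a whole to make percentage days abstinent secondary. It does not: its statistics paragraph agrees with the body, and one sentence is out of line.

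**Conclusion.** The contradiction is real and concerns a primary outcome. Protocol 13.3.2, followed as written, would count sub-threshold drinkers as relapsed, contrary to Protocol 4.1, SAP 5.2 and Table 2. It is a wording error against an operative definition, not an undetermined endpoint.

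Its numerical effect cannot be computed from the documents. It ranges from no change in the relative risk under assumption A to 0.59 instead of 0.50 under assumption B with q = 0.1. Both take the planning rates to be 5/4-drink rates, which the plan does not state. Under B the lower 90% limit for the difference moves from 2.8 to −0.4 points. No decision rule rests on that limit, so it shows sensitivity only.

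The inconsistency over percentage days abstinent is confined to one sentence in the Summary's design paragraph. The plan's intent that it be primary is clear elsewhere.

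**What to change.** Before the outcome data are analysed:

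1. In Protocol 13.3.2 and the SAP introduction, replace the bracketed any-drinking gloss on relapse with the 5/4-drink definition of Protocol 4.1 and SAP 5.2.
2. Complete the relapse derivation in SAP 5.3 with the same threshold. State the follow-up window and how a single occasion is read from daily timeline follow-back records. SAP 5.2 settles neither. Visit 10 can fall 23 to 25 weeks after visit 2 (161 to 175 days), so the window needs an explicit end.
3. In Protocol 13.2.1 and SAP 4.6, state which definition the 50% and 25% rates refer to. In 13.2.1, note that the 42-point pilot figure equals the 66% vs 24% abstinence difference in Protocol 2.3.
4. In the Summary's design paragraph, list 6-month percentage days abstinent as primary.

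Reporting any drinking as a further, separately labelled outcome is optional.

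The cost is a wording amendment to the protocol and a SAP revision. No new data are needed, because timeline follow-back (Protocol 7.9.1) already collects daily drinking.
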